6.5.2 PoM

The PoM is a 5-point rating scale that measures the patient's preference of study medication to previous medications to treat migraine pain from much better to much worse. Refer to the Zavegepant Core SAP for the 5 categories and additional combined categories.

PoM are tabulated as the number and percentage of subjects in each preference category (including combined categories) by as-randomized treatment group. Percentages are presented with exact Clopper-Pearson 95%. Analyses are provided for the following: (1) overall; (2) by pain freedom outcome at 2 hours postdose (responder, failure) for subjects who are included in the complete cases sensitivity analysis of pain freedom at 2 hours postdose (see Section 6.3.2.1).

A by-subject listing of PoM is provided for the enrolled analysis set.

6.6 COVID-19 Impact

Analyses are based on COVID-19 visit impact data with non-missing COVID-19 visit dates (see Section 9.1.1).

Measurements are slotted into analysis visits according to COVID-19 visit date (see Section 7.3).

6.6.1 COVID-19 Overall Impact

COVID-19 visit impact is tabulated by as-treated treatment group and overall for the safety analysis set. The number and percentage of subjects in the categories defined by COVID-19 visit impact type, visit impact characteristics, and visit impact relationship are tabulated (see Section 9.1.1). Percentages are based on subjects with ≥ 1 visit with non-missing COVID-19 visit impact (see Section 9.1.3).

6.6.2 COVID-19 Impact over Time

COVID-19 visit impact is tabulated by analysis visit (Screening, Randomization, End of Study) and as-treated treatment group for the safety analysis set. The number and percentage of subjects in the categories defined by COVID-19 visit impact type, COVID-19 visit impact relationship are presented for each analysis visit. Percentages are based on subjects with ≥ 1 visit with non-missing COVID-19 visit impact in the analysis visit window.

Missing LFT data impacted by COVID-19 are tabulated at each analysis visit for the safety analysis set as the number and percentage of subjects in the following categories:

- 1) Missing LFT data, defined as missing values for all of the 4 following LFTs in the analysis visit window: ALT, AST, ALP, and TBL.
- 2) Missing LFT data at visits impacted by COVID-19, i.e., meeting criteria (1) and having ≥ 1 visit impacted by COVID-19 in the analysis visit window (see Section 9.1.3)
- 3) Missing LFT data at missed visits due to COVID-19, i.e., meeting criteria (1), (2), and having ≥ 1 missed visit in the analysis visit window (see Section 9.1.1).

Percentages are based on evaluable subjects at each analysis visit. A subject is evaluable at an analysis visit if the study day corresponding to the last contact date is \geq lower bound of the analysis visit window. For subjects who took study drug but were not randomized, the treatment day corresponding to the last contact date is used instead.

6.6.3 COVID-19 Impact Listings

A by-subject listing of COVID-19 impact codes by visit displays visits (i.e., Screening, Randomization, End of Study) in separate columns for the enrolled analysis set. Each column denotes an analysis visit and displays the COVID-19 visit impact code (see Section 9.1.5.1). If a subject has multiple COVID-19 visit impact codes in an analysis visit window, then results are displayed sorted by visit date and comma-concatenated across all COVID-19 visit dates in the analysis visit window (e.g., “#,&UM1” if “#” has visit date of 01JUL2020 and “&UM1” has visit date of 10JUL2020). Visits during the on-treatment safety analysis period are identified. Footnotes describe the abbreviations in the COVID-19 visit impact code (see Section 9.1.5.2).

A by-subject listing of COVID-19 visit impact is provided for the enrolled analysis set (see Section 9.1.1). The listing displays analysis visit, COVID-19 visit date, study day derived from the COVID-19 visit date, treatment day derived from the COVID-19 visit date, visit impact status, visit type (scheduled or unscheduled), visit impact type, visit impact characteristics, visit impact relationship, and premature study termination (yes; no; not applicable, subject continuing).

7 CONVENTIONS

7.1 Derived Dates

Derived dates are defined as follows:

- Study drug start date/time: Earliest (1) study medication dose date and time from the eDiary Migraine Report, or (2) study medication intake date and time from the Study Medication Intake Report (see Section 7.5.1). This date is used to define analysis periods.
- Rescue medication start date/time: Earliest rescue medication date/time (see Section 6.2.6.2). Missing time is considered to be earlier than non-missing time on the same date.
- Imputed rescue medication start date/time: This is used only for time-to-event efficacy analyses in Section 6.3.4.3, and not for time to rescue medication use analyses in Section 6.3.3.8.
 - If the rescue medication start date and time are both not missing, then the imputed rescue medication start date/time is set to the rescue medication start date/time.
 - If the rescue medication start time is missing and the rescue medication start date is equal to the study drug start date, then the imputed rescue medication start date/time is set to the study drug start date/time.
 - Otherwise, if the rescue medication start time is missing and the rescue medication start date is equal to a postdose eDiary finding date with non-missing efficacy data, then the

imputed rescue medication start date/time is set to the first eDiary finding date/time corresponding to non-missing efficacy data.

- Otherwise, if the rescue medication start time is missing and rescue medication start date is equal to the study drug start date + 1 day, then the imputed rescue medication start date/time is set to the study drug start date/time + upper bound of the X -hour analysis window (see Table 5).
- COVID-19 visit date: (1) Complete visit date, if it exists; (2) otherwise, complete date the visit was planned to occur for a missed visit (see Section 9.1.1).
- Last contact date: (1) Earliest complete death date from AE CRFs, if it exists; (2) otherwise, the maximum complete date of the following: AE start or stop; COVID-19 visit only for in-person or remote visits; ECG; eDiary finding; eDiary study drug start; informed consent; IWRS randomization; laboratory collection; nasal inspection; non-study medication start or stop; physical measurement; procedure; rating scale; questionnaire; vital sign; visit. If the last contact date is after the most recent raw database creation date, then it is set to the most recent raw database creation date.
- Death date: Last contact date derived only for subjects who died (see Section 6.4.1).

No date imputations are performed on these derived dates. Complete dates are those with valid, non-missing day, month, and year.

7.2 Analysis Periods

Analysis periods are defined as follows:

- Pre-treatment: measurement date/time at or before the study drug start date/time. This period is used to derive baseline values and to assess pre-treatment endpoints. Note that all measurements are pre-treatment for subjects in the enrolled analysis set with missing study drug start date.
- On-treatment: measurement date/time after the study drug start date/time. This period is used to assess safety endpoints on treatment. Note that AEs with imputed start date equal to the study drug start date are part of this period.

See Section 7.1 for derived date/times for determining analysis periods.

If measurement time is missing, not collected, or not applicable for a parameter, then the measurement date is compared to the derived date.

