6.4.2 Laboratory Tests

Laboratory tests are analyzed using results from the external central laboratory CCI [REDACTED] which identifies expired kits, and from local laboratory tests reported on CRFs. The central laboratory reports both laboratory collection date and time, whereas CRFs capture only laboratory collection date.

Clinically significant laboratory abnormalities are identified as grade 3 to 4 laboratory test results. Refer to the Zavegepant Core SAP for laboratory tests of clinical interest for analyses, including identification of those with toxicity grades.

The following by-subject laboratory test listings are provided for the enrolled analysis set:

- Select laboratory test groups: hematology (both SI and US units)*; serum chemistry (both SI and US units)*; urinalysis (US units only)*; pregnancy (US units only)*; endocrinology, serology, drug screen, and miscellaneous laboratory tests (US units only). The pregnancy listing identifies positive pregnancy tests, which are defined as serum or urine pregnancy tests with either (a) “positive” character value, or (b) numeric value ≥ 25 U/L.
- Liver function test (LFT) values and ratios to ULN (i.e., alanine aminotransferase [ALT], aspartate aminotransferase [AST], total bilirubin [TBL], and alkaline phosphatase [ALP]) for both US and SI units*. The listing displays all LFT results over time for subjects with select LFT elevations (ALT or AST $> 3x$ ULN; ALP or TBL $> 2x$ ULN) at any time point.

- Creatine kinase (CK) elevation questionnaire.

Listings display toxicity grades and identify expired kits from the central laboratory, if applicable, and those marked with “*” display COVID-19 visit impact code for visits impacted by COVID-19 (see Section 9.1.5.2). Refer to the Zavegepant Core SAP for listing contents.

6.4.2.1 *Laboratory Test Abnormalities*

On-treatment laboratory test abnormalities are tabulated as the number and percentage of subjects in the safety analysis set in the following frequency tables:

- Worst (highest) on-treatment laboratory test abnormality for each graded laboratory test.
- Laboratory test toxicity grade shift from baseline to the worst on-treatment toxicity grade for each graded laboratory test.
- Laboratory test low/normal/high shifts from baseline to any abnormal on-treatment value for each laboratory test with normal ranges.

Refer to the Zavegepant Core SAP for toxicity grade categories and additional details.

6.4.2.2 *Liver Function Test Elevations*

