6.4.3 Vital Signs and Physical Measurements

All parameters are reported with measurement date only (no time).

Vital signs include systolic blood pressure, diastolic blood pressure, heart rate, temperature, and respiratory rate.

Physical measurements include height (collected at screening only), weight, and BMI.

A by-subject listing of vital signs and physical measurements is provided for the enrolled analysis set, and displays COVID-19 visit impact code for visits impacted by COVID-19 (see Section 9.1.5.2).

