6.4.4 Electrocardiogram

ECG parameters include RR, QRS, PR, QT, QTcF, and ventricular heart rate, which are measured with both date and time by the external source CCI

A by-subject listing of ECG results is provided for the enrolled analysis set, and displays COVID-19 visit impact code for visits impacted by COVID-19 (see Section 9.1.5.2).

6.4.4.1 *ECG Changes from Baseline*

Values and changes from baseline in ECG parameters are tabulated as continuous variables at baseline and the end of treatment visit.

If there are multiple values on the same measurement date and time, then the value with the last ECG reference identifier is used.

6.4.4.2 *ECG Interpretation Shifts from Baseline to Worst Category*

ECG interpretation shifts from baseline to the worst on-treatment category are tabulated as the number and percentage of subjects with normal, abnormal, and clinically significant abnormal interpretations.

6.4.4.3 *ECG Abnormalities*

On-treatment ECG abnormalities are tabulated as the number and percentage of subjects in the categories specified in the Zavegepant Core SAP.

6.4.5 **S-STS**

The S-STS is a prospective rating scale that contains 16 patient-reported questions and 6 clinician-reported questions to track both treatment-emergent suicidal ideation and behaviors. Refer to the Zavegepant Core SAP for calculation of the S-STS ideation subscale, behavior subscale, and total scores.

Values and changes from baseline in the self-reported S-STS ideation subscale, behavior subscale, and total score are tabulated as continuous variables at baseline and the end of treatment visit. The number and percentage of subjects in each change from baseline category (i.e., < -1, -1, no change, 1, > 1) are also presented for the ideation subscale, behavior subscale, and total score.

A by-subject listing of S-STS is provided for the enrolled analysis set, and displays COVID-19 visit impact code for visits impacted by COVID-19 (see Section 9.1.5.2).

Refer to the Zavegepant Core SAP for the listing contents.

6.4.6 **Safety Narratives**

A by-subject listing of safety narrative subject identifiers is provided for the following select events and analysis sets as columns:

- All deaths for the enrolled analysis set
- On-treatment SAEs for the safety analysis set treated with zavegepant
- All AEs leading to discontinuation of study drug for the safety analysis set treated with zavegepant

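### Under SAP 7.2, an unscheduled postdose vital sign or local laboratory value dated on the dosing day is classed as pre-treatment: it can become the baseline and is left out of the on-treatment tables

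*SAP*

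**What the plan says.** SAP 7.2 defines two periods. One is "Pre-treatment: measurement date/time at or before the study drug start date/time"; the other is "On-treatment: measurement date/time after the study drug start date/time". Where a finding has no time, the rule is: "If measurement time is missing, not collected, or not applicable for a parameter, then the measurement date is compared to the derived date". The section gives one same-day exception, for adverse events: "Note that AEs with imputed start date equal to the study drug start date are part of this period". It gives none for findings.

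Which findings lack a time is stated elsewhere. SAP 6.4.3 says that vital signs and physical measurements carry a date only. For laboratory tests, SAP 6.4.2 says: "The central laboratory reports both laboratory collection date and time, whereas CRFs capture only laboratory collection date". ECG parameters are different (SAP 6.4.4): "which are measured with both date and time by the external source".

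SAP 6.2.5 takes the last non-missing pre-treatment value as baseline for the safety analysis set. The vital sign abnormality table (6.4.3.2), the laboratory abnormality and shift tables (6.4.2.1), and the LFT shift table and eDISH plot (6.4.2.2) draw on on-treatment values. LFT elevations are tabulated separately for each period. SAP 6.4 also refers to the Zavegepant Core SAP for slotting safety parameters into periods; that document is not among those supplied.

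**The concern.** When only dates are compared, a value dated on the dosing day equals the study drug start date. It is therefore pre-treatment, whether it was taken before or after the dose. If a subject is seen for a reaction a few hours after the single dose, the blood pressure or local laboratory result from that visit is filed as pre-treatment, while the reaction itself, recorded as an AE with that date, is on-treatment.

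Two things are at stake in the safety tables. The postdose value does not count as an on-treatment abnormality. And if it becomes the baseline, the change at the end of treatment visit is measured from a value that the drug may already have affected, so a return to normal reads as an improvement. The error runs one way: it takes findings close to the only dose out of the on-treatment outputs.

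**Working it through.** The point rests on no figure in the plan, so there is none to reproduce. The check applies the rules of SAP 7.2, 6.2.5 and 7.3 (Table 4) to test records.

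**Inputs**
- Period (7.2): pre-treatment if measurement ≤ study drug start, on-treatment if later; dates alone are compared when there is no time.
- Baseline (6.2.5): the latest pre-treatment value.
- Study day (7.3): measurement date − randomization date + 1, on or after randomization. Study day 1 is the Randomization window; study day 2 or later is the end of treatment window.

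**Test subject:** randomized 1 March, dosed 10 March at 09:00.

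| Record | Time held? | Period | Study day | Table 4 window |
|---|---|---|---|---|
| Randomization visit vital signs, 1 March | no | pre-treatment | 1 − 1 + 1 = 1 | Randomization |
| Unscheduled vital signs or local laboratory value, 10 March 15:00 | no | **pre-treatment** | 10 − 1 + 1 = 10 | **end of treatment** |
| Central laboratory value or ECG, 10 March 15:00 | yes | on-treatment | 10 | end of treatment |
| AE with imputed start date 10 March | not needed | on-treatment (stated exception) | not applicable | not applicable |
| Vital signs or local laboratory value, 11 March | no | on-treatment | 11 − 1 + 1 = 11 | end of treatment |
| End of treatment visit, 17 March | no | on-treatment | 17 − 1 + 1 = 17 | end of treatment |

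**Results**
1. Of two values taken at the same moment, six hours after the dose, the one with a time is on-treatment and the one without is pre-treatment. The class depends on the data source.
2. The latest pre-treatment vital sign is the 10 March postdose value, so it replaces the 1 March value as baseline. For laboratory tests it would replace the screening value, because Protocol Table 1 schedules safety laboratory tests only at Screening and end of treatment.
3. Write b for the true predose value, p for the postdose dosing-day value and e for the end of treatment value. The change reported is e − p, where e − b was intended. The error is (e − p) − (e − b) = b − p, the whole of the acute change with its sign reversed.
4. The 10 March value is baseline by period and end of treatment by visit window. SAP 6.4.2.3 picks the last viable laboratory value in that window and states no limit by period. If no later laboratory value exists, one result can serve as both, with a change of zero.

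**Where the rule works:** a subject randomized in clinic and dosed at home later the same day has predose clinic vital signs dated on the dosing date. SAP 7.2 rightly keeps these as pre-treatment. Simply reversing the rule would misclass them.

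**How often:** Protocol Table 1 has no vital sign or laboratory test between dosing and the end of treatment visit, and that visit follows the handheld assessments, which run to 48 hours (Protocol 4.3.2, 4.3.5). Only unscheduled dosing-day measurements are affected, and the documents give no count. As an assumption only, 0 to 5 subjects against the 1,260 planned as evaluable for efficacy (a rough stand-in for the number treated) is 0/1,260 = 0% to 5/1,260 = 0.4%.

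**The case against.** The strongest reply is that the rule may not be complete as printed. SAP 6.4 sends the reader to the Core SAP for exactly this slotting, and a same-day or unscheduled-visit rule could be there. This stands as a condition on the point. It does not remove it: SAP 7.2 is this study's own definition, and it states an exception for AEs and nothing for findings.

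The second reply is that the schedule produces no such value and that the convention has a purpose, namely the subject dosed later on the randomization day. Both parts stand, and they limit the size of the problem and the form of the fix. The protocol does leave room for the case. Subjects are told to contact the site at once about a severe or serious event (synopsis, Study Design), and clinically significant local laboratory results must go into the CRF (Protocol 6.3.4), which is the source without a time. AEs and findings may reasonably follow different rules, since only findings need a baseline, so the AE exception alone does not show an error.

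Third, a reader might infer that acute reactions disappear from the safety results. The documents do not support that. Listings keep the value and show its treatment day (SAP 6.1.1.2), which would be 1. A dosing-day LFT elevation appears in the pre-treatment LFT table (6.4.2.2). Clinically significant laboratory results are also to be captured as AEs or SAEs (Protocol 8.2.2), and those dated that day are on-treatment. What remains is narrower. The listings identify on-treatment data (SAP 6.4), and this value would not be so identified. The LFT triggers for narratives cover on-treatment events only (6.4.6), so that route would miss it.

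Fourth, a reader might infer that the value always becomes the baseline, or that every date-only value on the dosing day is misclassified. Neither follows. With two vital signs on one date the last entered is used (6.4.3.1). For laboratory tests, a viable central value ranks above a local one on the same date (6.4.2.3, cited by 6.2.5). Predose values on that day are classed correctly.

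**Conclusion.** The point holds as a gap in a stated rule. Read with SAP 6.4.2, 6.4.3 and 6.2.5, SAP 7.2 puts an unscheduled, postdose, date-only value from the dosing day in the wrong period. The value can become the baseline, and it drops out of the on-treatment abnormality, shift, eDISH and vital sign outputs.

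The effect is small in number and confined to descriptive safety outputs; no efficacy endpoint or test is touched. Any count of affected subjects is an assumption, and zero is compatible with the documents. It would also go too far to say that such values must come from acute reactions: that is the plausible reason for an unscheduled visit on the dosing day, but the documents do not show it.

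The conclusion assumes that the Core SAP has no overriding rule. The correction is worth making before database lock because it is cheap and because the error always takes postdose findings out of the on-treatment outputs.

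**What to change.** First check the Core SAP. If it already handles date-only findings on the dosing day, add a cross-reference in SAP 7.2 and stop there.

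Otherwise add to SAP 7.2: a finding without a time, dated on the study drug start date, is pre-treatment if it was collected at the Screening or Baseline/Randomization visit; otherwise it is on-treatment and cannot be used as baseline. In the test case this moves the 10 March value to on-treatment and restores the 1 March vital signs as baseline. It agrees with the Table 4 window, and it leaves clinic values correct for a subject dosed later on the randomization day.

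Identify the visit from the record's visit label. SAP 9.1.1 recognizes unscheduled visits by label, but only in describing the COVID-19 Visit Impact CRF, so confirm that vital sign and local laboratory records carry one. If they do not, compare the record's date with the randomization date: a dosing-day value dated after randomization is on-treatment. That fallback cannot separate predose from postdose values for a subject dosed on the randomization day itself.

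The cost is one sentence and one programming condition, plus the label check. The downside is that a rare unscheduled predose value on the dosing day would count as on-treatment, the direction the SAP already takes for AEs.

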7.3 Analysis Visit Windows

Study days are calculated from the IWRS randomization date as follows:

- Measurement date – randomization date + 1, if measurement date \geq randomization date
- Measurement date – randomization date, if measurement date $<$ randomization date.

Treatment days are calculated from the study drug start date as follows:

- Measurement date – study drug start date + 1, if measurement date ≥ study drug start date
- Measurement date – study drug start date, if measurement date < study drug start date.

Analysis visit windows for safety parameters are presented in [Table 4](#).

Table 4: Analysis Visit Windows for Safety Parameters

Analysis Visit	Analysis-Specified Interval
Screening	
 • ≤ Study day -1 or {both study day and treatment day missing} • ≤ Treatment day -1 *
Randomization	Study day 1
End of treatment	
 • ≥ Study day 2 • ≥ Treatment day 1 *

* Applies only to subjects who took study drug but were not randomized

See Section [7.5.2](#) for efficacy analysis windows and Section [7.5.3](#) for outcomes research analysis windows.

